**Protocol**

**09/16/09**

**Background**

VT is the next frontier in electrophysiology. An increasing number of patients require VT ablation despite optimal medical therapy. Myocardial scars are present in the majority of patients with ischemic and nonischemic cardiomyopathy and usually act as the substrate for reentrant VT. According to pathological findings, rather than being homogeneous tissue, cardiac scars often contain many “channels” of surviving myocardium within the area, which enable electricity to enter, traverse, and exit the scar via different connections within this network and form a “reentry loop” maintaining reentrant VT. Cauterizing the myocardial channels along the scar border in order to interrupt those loops and clinical VT, therefore, is the aim for most reentrant VT ablations. Because of hemodynamic intolerance as well as the pre-existing alternative channels and exit sites, an approach targeting single VT channels identified by their electrical characteristics will not be applicable for the majority of patients. A “substrate-guided” ablation approach is frequently conducted to treat such arrhythmias and involves the placement of linear ablation lesions along the scar

**HP00043324**  
**NCT01250912**

border in order to interrupt as many channels as possible. These are the most commonly used and accepted treatment strategies.

**HP00043324**  
**NCT01250912**

A detailed anatomic knowledge of scar location and exact scar borders is necessary to accurately place curative ablation lines. 3D mapping systems are currently used to create a “voltage map” of the left ventricle (LV) to obtain such anatomic information (current “gold standard”). The amplitude of endocardial voltages is measured and recorded in real time by a roving mapping catheter moved along the endocardial LV surface. However, voltage mapping has several important limitations: First, endocardial voltage is limited in distinguishing between nonviable and damaged but viable myocardium. Second, a single endocardial voltage measurement cannot differentiate between endocardial and epicardial scar components. Third, suboptimal catheter contact can result in falsely low voltage measurements leading to an overestimation of ventricular scar and unnecessary ablation lesions. Fourth, the limited spatial resolution of the catheter tip and the mapping density of the voltage map can make the detection of isolated scar areas or small patches of surviving myocardium (which could represent viable VT channels)

**HP00043324**  
**NCT01250912**

difficult. Finally, detailed voltage mapping is quite time consuming, which increases procedure length and complication rates.

Current research focuses mostly on better defining the myocardial scar with metabolic or anatomic imaging. However, this has multiple limitations. Magnetic resonance (MR) imaging has been validated to assess anatomic information about scar but is currently contraindicated after implantable cardioverter-defibrillator placement and thus unavailable in nearly all patients requiring VT ablations. Metabolic imaging can provide an alternative definition of myocardial scar to voltage mapping, but will still rely

**HP00043324**  
**NCT01250912**

on the same therapeutic approach of creating linear lesion along the scar border, which has only a limited long-term success rate of 53%.

Abnormal sympathetic cardiac innervation has been shown to have prognostic value for different heart diseases, e.g. heart transplant, coronary artery disease, heart failure, arrhythmias, etc. Importantly, there is a clear association with an increased cardiac morbidity and mortality in ischemic heart diseases. I-metaiodobenzylguanidine (I-MIBG) allows visualization of the cardiac innervation, which could provide additional information to understand VT.

Therefore, the clinical need exists for a novel approach, which could provide new pathophysiological insights and may provide

**HP00043324**  
**NCT01250912**

innovative treatment strategies. Given a well established relationship between ventricular arrhythmias/sudden cardiac death and the cardiac innervation we propose to investigate the relationship between MIBG innervation imaging and ventricular ablation procedures.

### **Objective of the study**

The purpose of this study is to assess if Single Photon Emission Computed Tomography (SPECT) demonstrating cardiac innervation can be integrated into current electrophysiology voltage mapping system and provide improved guidance for ablation of ventricular tachycardia.

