**Research Part of the Protocol**

Four specific aims were plan to achieved for this research. Specific Aim 1: Evaluate if areas of left ventricular (LV) denervation measured by cardiac 123I-metaiodobenzylguanidine (MIBG) SPECT imaging (innervation map) can be integrated into the CartoXP electrophysiology mapping system. Specific Aim 2: Evaluate, in a group of 20 patients, if areas of denervation in the 3D maps reconstructed from MIBG SPECT imaging correlate with the voltage-map defined scar targeted during VT ablations Specific Aim 3: Determine the changes of cardiac innervation before and 6 months after the VT ablation in 20 patients. Specific Aim 4: Investigate the possible predicting factors for VT reoccurrence within six month after the ablation.

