**Measures to Reduce Risks**

Our approach will be to conduct the cardiac imaging scan and reconstruction for the patients first. This will be followed by endocardial mapping. The imaging information known before the endocardial procedure will help reduce the mapping time, improve the mapping/ablation accuracy and reduce the risk due to the long procedure time. It is our belief that, with this imaging guidance approach, we can improve the success rate of VT ablation in VT patients.

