**HP00043324**  
**NCT01250912**

Differences in scar size, morphology and severity between 3D MIBG innervation maps and EP voltage maps will be analyzed using Student T-test. Segments where diastolic potentials, fractionated potentials and successful ablation sites are located will be investigated in order to identify the characteristics of the MIBG imaging in those segments, e.g. heterogeneity, etc. Segmental/regional washout rate, normalized MIBG activities as well as SS scores will be compared with segmental/regional voltage values in order to identify the relationship between cardiac denervation areas and abnormal endocardial voltage areas.

Differences in size, morphology and severity, regional/global washout from planar images, normalized regional intensities, regional activity summed scores between pre and post ablation 3D MIBG innervation maps will be analyzed using Paired T-test. Global wash out rate will be correlated with HRV indexes before and after the ablation to investigate the relationship between them. Normalized regional MIBG intensities, regional wash out rate and regional SS score both before and after ablations will be compared between VT exit sites segments and other segments with independent sample T-test in order to identify the innervation characteristics of the exit site segments.

Measurements and results will be reported as mean  $\pm$  standard deviation if a normal distribution can be assumed. P values at a level of  $<0.05$  will be considered as statistically significant. Pearson correlation will be conducted to investigate the relationship between two sets of images. The logistic regression will be conducted to investigate the relationship between 3D innervation morphologies, HRV parameters, patient characteristics, clinical VT characteristics and the VT recurrence within the six month

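### The guidance half of the objective has no analysis: MIBG and voltage maps are compared only for agreement, and voltage is never assessed at the VT sites where MIBG is examined.

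*Combined protocol and SAP*

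**What the plan says.** The Objective section joins two questions: whether MIBG SPECT "can be integrated into current electrophysiology voltage mapping system and provide improved guidance for ablation of ventricular tachycardia".

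The Research Part of the Protocol turns this into four aims: integration into the mapping system, correlation of denervation with voltage-defined scar ("Evaluate, in a group of 20 patients, if areas of denervation"), change in innervation at 6 months, and predictors of recurrence. None is worded as a test of guidance.

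The Data Analysis section plans:

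- means and SDs for four registration strategies;
- map against map: "Differences in scar size, morphology and severity between 3D MIBG innervation maps and EP voltage maps will be analyzed using Student T-test", Pearson correlation, and segmental MIBG measures set against segmental voltage "in order to identify the relationship between cardiac denervation areas and abnormal endocardial voltage areas";
- MIBG at arrhythmia sites: "Segments where diastolic potentials, fractionated potentials and successful ablation sites are located will be investigated" to describe the MIBG image there, and MIBG measures in exit-site segments against other segments by t-test;
- pre/post paired tests, correlation of washout with HRV, and logistic regression for six-month recurrence;
- one sentence on ROC curves for the innervation and voltage maps.

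Under Measures to Reduce Risks, all patients are imaged before mapping ("Our approach will be to conduct the cardiac imaging scan and reconstruction for the patients first"). The investigators state the belief that with this approach "we can improve the success rate of VT ablation in VT patients".

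**The concern.** Agreement and added value are different quantities. If the MIBG map reproduced the voltage map exactly, every planned agreement measure would be as good as it could be, and MIBG would tell the operator nothing new. If MIBG flagged arrhythmia sites that voltage misses, agreement would fall. The planned map-to-map comparisons therefore cannot answer the guidance question in either direction.

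The site analyses come closer, because they ask whether MIBG differs where the arrhythmia arises. But they have no voltage counterpart, so they cannot say whether MIBG carries information beyond the map already in use.

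At stake is the interpretation. A good correlation, or an MIBG difference at exit sites, could be reported under an objective about improved guidance although no result in the plan bears on improvement.

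**Working it through.** **1. Analyses set against the objective.** The plan gives no power, effect size, SD or sample-size rationale, so there is no stated calculation to reproduce. The main check is structural.

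| Planned analysis | Question it answers | MIBG versus voltage as a guide? |
|---|---|---|
| Registration strategies | Integration | No |
| t-test, Pearson, segmental relationship | Agreement of the maps | No |
| MIBG at abnormal-potential and successful-ablation segments | MIBG features at sites | No, voltage absent |
| MIBG, exit-site against other segments | MIBG difference at sites | No, voltage absent |
| Pre/post tests, HRV correlation | Change over 6 months; link with HRV | No |
| Logistic regression | Prognosis; voltage is not among the listed predictors | No |
| ROC sentence | Unclear: no reference outcome, unit of analysis or AUC contrast | Cannot be determined |

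**2. Are the data there?** The Voltage Map Dataset section divides each map into 17 segments, with normal above 1.5 mV. The 123I-MIBG Imaging Dataset section scores 17 segments from 0 to 4. The Data Analysis section locates the sites by segment. In 20 patients this gives 20 × 17 = 340 segment pairs, clustered in 20 patients. A paired site comparison is therefore possible. Procedure and mapping times are not listed as collected, and there is no comparator group.

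**3. Precision of a paired capture difference.** Assume one index site per patient, n = 20. Let a be the share of sites flagged by MIBG only and b the share flagged by voltage only. The rates below are assumptions.

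SE = √{[a + b − (a − b)²]/n}; half-width = 1.96 × SE (large-sample approximation).

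| a, b | Difference | SE | 95% half-width | Exact McNemar power |
|---|---|---|---|---|
| 0.20, 0.05 | 15 points | √(0.2275/20) = 0.107 | 21 points | 10% |
| 0.30, 0.10 | 20 points | √(0.36/20) = 0.134 | 26 points | 17% |
| 0.40, 0.10 | 30 points | √(0.41/20) = 0.143 | 28 points | 37% |
| 0.50, 0.10 | 40 points | √(0.44/20) = 0.148 | 29 points | 57% |

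The last column is by binomial enumeration at two-sided 0.05 (the plan sets 0.05 without stating sidedness). For the last three rows, 80% power would need about 84, 46 and 30 patients.

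**4. Ceiling from site selection.** Aim 2 says the voltage-defined scar is what is targeted, so successful sites will tend to lie in voltage-abnormal tissue. If voltage flags a share v of the sites, then a ≤ 1 − v. Taking b = 0, the case most favourable to MIBG:

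| v (assumed) | Largest difference | In 20 patients | Exact p for that split | Largest power |
|---|---|---|---|---|
| 0.90 | 10 points | 2 v 0 | 2 × 0.5² = 0.50 | 1% |
| 0.80 | 20 points | 4 v 0 | 2 × 0.5⁴ = 0.125 | 20% |
| 0.70 | 30 points | 6 v 0 | 2 × 0.5⁶ = 0.031 | 58% |

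The largest power is P(X ≥ 6) for X binomial(20, 1 − v), since at least six discordant patients, all in one direction, are needed for p < 0.05. A non-significant test at successful sites could simply reflect how the sites were chosen.

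**5. Segment-level AUC.** Simulation with 20 patients × 17 segments, 1 to 3 target segments each, within-patient correlation 0.25 and between-map correlation 0.3 to 0.6 (all assumed) gave an SE of the AUC difference of 0.031 to 0.059. The 95% half-width is 0.06 to 0.12. Power for 0.80 against 0.70 was 40% to 86%. This uses more of the data than one site per patient, but it is still imprecise.

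**The case against.** The strongest reply is that this is a 20-patient, single-group imaging study that describes itself as an investigation of a relationship, and that an ambitious purpose sentence needs only rewording. Several parts of that reply stand.

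- The objective is to assess, not to show, and its integration half is properly addressed. A reader might infer that the study cannot answer its objective at all. That is true of one half only.
- A reader might infer that MIBG is judged solely by how well it matches voltage. The documents do not support this: exit-site, abnormal-potential and successful-ablation segments and recurrence are all examined without voltage as the reference. Half of the needed site table is already planned.
- A reader might set recurrence against the 53% long-term success rate in the Background and treat that as the missing test. No section makes 53% a benchmark. It describes long-term results of linear scar-border lesions, whereas recurrence here is assessed at six months and used only to look for predictors.
- The sentence about improving success is a stated belief in a section on risk, not a hypothesis or endpoint.
- A significance test at successful sites would be a poor remedy, because it favours voltage by selection and has low power.

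What does not stand is that rewording alone is the best response. The missing half is the voltage column at sites already located on the same 17 segments. Adding it gives a direct, if imprecise, estimate on the guidance question.

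**Conclusion.** The concern holds for the guidance half of the objective. No aim or specified analysis compares MIBG with voltage in locating VT sites, and the ROC sentence is too incomplete to count. This rests on reading the whole Data Analysis section and needs no numerical assumption.

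The size of the remedy is modest. At n = 20 a paired comparison can only be estimation: half-widths of about 21 to 29 percentage points for capture, or 0.06 to 0.12 for AUC, under the assumed discordance rates and correlations. Neither map is independent of site selection. Voltage helps define the target, and the MIBG image is known before mapping. Exit sites are probably less affected by targeting than successful ablation sites, but the plan does not say how exit sites are determined, so this is an assumption.

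The change is worth making and does not undermine the other aims. The documents support no conclusion about procedure time or ablation success, and the added analysis would not change that.

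**What to change.** Extend the planned site analysis so that voltage is assessed at the same segments as MIBG.

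1. **Sites.** Use VT exit-site segments as primary and successful-ablation segments as secondary. State how each is located and how patients with several sites are handled.
2. **Flags.** For each segment record whether voltage flags it (the plan's 1.5 mV limit) and whether pre-ablation MIBG flags it (a cut-off on the 0–4 score fixed in advance). Also fix in advance how point voltages become one segment value, whether the early or the 4-hour SPECT is used, and how non-assessable segments are treated.
3. **Report.** Give the paired table, each map's capture rate, and the share of LV segments each map flags, since a map flagging all 17 segments captures every site. Give the paired difference in capture, or in AUC with site status as the reference, with a patient-clustered 95% CI. Label it exploratory estimation, without a McNemar significance test. If AUC is chosen, rewrite the ROC sentence to match.
4. **Limits to state.** Successful sites favour voltage because voltage-defined scar is targeted; the MIBG image is known before mapping; precision is low at n = 20.
5. **Conclusions.** Restrict the objective and conclusions to integration, association and this measure, with no claim of shorter procedures or better success from this single group.

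The cost is one extra table, a few definitions fixed beforehand, and a narrower claim supported by an imprecise estimate. No new patients or measurements are needed.

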### **Benefits to the Patient**

Direct benefits to the participant would be the possibility of reducing VT ablation procedure time. Indirect benefits include the possibility of reducing VT ablation

procedure time and increasing the accuracy of the ablation location with an overall improvement in the quality of life.

### **Study Population**

#### **Inclusion Criteria:**

1. Patients with ventricular arrhythmias requiring VT ablation
2. Age 18 y and above;
3. Ability to sign informed consent.

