#### **Exclusion criteria:**

1. Younger than 18 y;
2. Inability to sign informed consent.

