**Voltage Map Dataset**

All voltage maps will be created by an electrophysiologist using a Carto 3D mapping system and a 3.5-mm Navistar cooled-tip catheter. Bipolar electrograms will be filtered at 10–30 to 400–500 Hz. Standard clinical voltage criteria will be used to define scar (<0.5 mV), abnormal (0.5–1.5 mV), and normal (>1.5 mV) myocardium. Each voltage map will be divided into 17 segments according to the AHA LV model to conduct visual analysis as well as quantitative analysis.

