**HP00043324**  
**NCT01250912**

### **123I-MIBG Imaging Dataset**

For the planar images a whole-heart region of interest (ROI) will be drawn manually to include both ventricles. A square mediastinal ROI (7x7 pixels) will be drawn in the upper mediastinum, using the apices of the lungs as anatomic landmarks. The H/M ratio will be calculated as the ratio of the counts per pixel in the two ROIs. H/M data will be used to calculate myocardial washout using two formulas. Uncorrected washout will be calculated as

$$H/M (early) - H/M (late) / H/M (early).$$

Background corrected washout will be calculated as

$$H (early) - M (early) - H (late) - M (late) / H (early) - M (early)$$

Single aggregate values for each washout parameter will be determined as described above.

For the SPECT image sets, segmental myocardial activity will be scored using a 17-segment model. Each segment will be scored using the following scale: 0 normal tracer uptake, 1 mildly reduced uptake, 2 moderately reduced uptake, 3 severely reduced uptake, 4 absent tracer uptake, NA not assessable. Accordingly, the summed score (SS) for each study could range from 0 to 68 (17x4).

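### Eligibility does not restrict chamber of origin, but the segmental and innervation-map measures cover the LV only; any RV-origin VT patients would distort the exit-site test and dilute the LV-segment parts of Aims 3 and 4

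*Combined protocol and SAP*

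**What the plan says.** Inclusion criterion 1 of the combined protocol and SAP reads "Patients with ventricular arrhythmias requiring VT ablation". The Exclusion criteria list only age under 18 and "Inability to sign informed consent". Neither list mentions chamber of origin.

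The segmental measurements are left-ventricular:

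- Background describes the voltage map as one "of the left ventricle (LV) to obtain such anatomic information".
- Voltage Map Dataset: "Each voltage map will be divided into 17 segments according to the AHA LV model".
- 123I-MIBG Imaging Dataset, for SPECT: "segmental myocardial activity will be scored using a 17-segment model". Each segment scores 0 to 4 or not assessable, and the sum runs from 0 to 68. No RV segment is defined.
- Research Part of the Protocol, Aim 1: "Evaluate if areas of left ventricular (LV) denervation measured by cardiac" MIBG SPECT can be integrated into the mapping system.

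Not everything is LV-only. The same imaging section draws the planar heart region around both ventricles, and the H/M ratio and washout come from it.

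Under Data Analysis, regional MIBG intensity, washout and summed score are "compared between VT exit sites segments and other segments with independent sample T-test". No rule covers a patient whose exit site lies outside the 17 segments. Patient Characteristics lists VT morphology among the items collected, but not chamber of origin.

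**The concern.** The entry criteria and the segmental measurements describe different populations. For a patient whose VT arises in, and is ablated from, the RV, the exit site and the lesions lie outside the 17 segments. Three analyses are exposed:

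- **Exit-site test.** The patient contributes only to the 'other' group. If LV uptake in such hearts differs from uptake in LV-VT hearts, the pooled test mixes a between-patient difference into what is reported as an exit-site difference.
- **Aim 3, LV-segment measures.** If the ablation leaves the measured myocardium unchanged, the patient pulls the mean pre/post change toward zero.
- **Aim 4, innervation-map predictors.** LV innervation is related to recurrence of an arrhythmia from another chamber, which weakens any real association.

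**Working it through.** **Inputs from the document.** 20 patients (Aims 2 and 3), 17 segments per map, significance level 0.05. The 20 comes without power, effect size, SD or dropout, so there is no sample-size figure to reproduce.

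**Assumptions.** k RV-VT patients among the 20, with k from 0 to 6; one exit segment per LV patient; all segments assessable; two-sided tests.

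**Segment counts.** There are 20 × 17 = 340 segments. Exit segments number 20 − k. Other segments number 16(20 − k) + 17k = 320 + k, of which 17k come from RV patients. Seventeen per patient is a maximum, because segments may be scored not assessable.

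**Exit-site bias.** Suppose there is no true exit effect and LV uptake in RV patients differs by D segment SDs. The expected difference between other and exit segments is then D × 17k/(320 + k). The false-positive rate of the pooled t-test was simulated with 4,000 runs per setting.

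| k | Exit / other | RV share of other | Bias | False positives, independent segments (D=1 / D=2) | False positives, within-patient correlation 0.3 (D=1 / D=2) |
|---|---|---|---|---|---|
| 2 | 18 / 322 | 34/322 = 10.6% | 0.11D | 6% / 8% | 3% / 5% |
| 4 | 16 / 324 | 68/324 = 21.0% | 0.21D | 10% / 20% | 7% / 16% |
| 6 | 14 / 326 | 102/326 = 31.3% | 0.31D | 15% / 34% | 13% / 35% |

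With correlation 0.3 and no RV patients, the rate is about 2%. With D = 0, the independent-segment rate stays near 5% at every k, so RV patients inflate it only when their LV uptake differs.

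**Exit-site power.** For a true difference of 0.65 SD, counting segments as independent, power is 80.5%, 76.5%, 71.8% and 66.3% for k = 0, 2, 4 and 6. This loss comes from having fewer exit segments, so leaving RV patients out does not recover it.

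**Aim 3, LV-segment change.** A paired t-test on 20 patients has 80% power at d = 0.66 SD. Suppose a share p = k/20 has no LV change. The mean is then d(1 − p), the SD is √(1 + d²p(1 − p)), and power follows from the noncentral t distribution.

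| k | Standardised effect | Power, all 20 | Power, LV patients only |
|---|---|---|---|
| 0 | 0.66 | 80% | 80% (n=20) |
| 2 | 0.594/1.019 = 0.58 | 70% | 75% (n=18) |
| 4 | 0.528/1.034 = 0.51 | 58% | 70% (n=16) |
| 6 | 0.462/1.045 = 0.44 | 47% | 63% (n=14) |

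A direct simulation at 0.65 SD with fixed numbers of RV patients agrees: 79%, 69% and 57% for k = 0, 2 and 4, and 73% and 68% for 18 and 16 LV patients alone. Under these assumptions, including the RV patients costs more power than leaving them out.

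**The case against.** The harm is conditional. The document gives no expected RV share, effect size, SD or power target, and the Background discusses scar-related reentry and LV voltage mapping, so the intended population may already be LV VT. With two RV patients and D = 1, the exit-site false-positive rate barely moves. Replacing an LV patient by an RV patient raises the 'other' count by only one segment. The test's deeper weakness is pooling segments across patients, which a within-patient comparison cures without changing eligibility.

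Most of this stands, and it limits the size of the point. It does not remove the mismatch, because the criteria do admit these patients and the analysis has no rule for them.

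Two stronger readings are tempting, and the document supports neither.

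- A reader might infer that every measure is LV-only, so that all of Aims 3 and 4 is diluted and RV patients should leave both aims entirely. Planar H/M and washout cover both ventricles, and planar washout is one of the pre/post outcomes. In Aim 4, only one of four predictor groups (the 3D innervation morphologies) is tied to the LV map; HRV, patient characteristics and clinical VT characteristics are not.
- A reader might infer that RV patients would undergo LV mapping purely for research. No section orders that.

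**Conclusion.** The point holds for the LV-segment and innervation-map analyses, provided RV-VT patients enrol. With an assumed 2 to 4 of 20, they supply 10.6% to 21.0% of the 'other' segments. The spurious exit-site difference is 0.11D to 0.21D. At four patients and D of 1 to 2, the false-positive rate is about 10% to 20% with independent segments, or 7% to 16% with correlation 0.3. Both the sign and the size of D are unknown; a difference in one direction could create a false exit effect, and in the other could mask a true one.

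Power for LV-segment change in Aim 3 falls from 80% to 70% or 58%, assuming a 0.66 SD effect in LV patients and none in RV patients. The weakening of the Aim 4 innervation predictors is argued here, not quantified. If no RV-VT patient enrols, nothing is lost. No figure stated in the document is wrong. This is an inexpensive improvement to the plan.

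**What to change.** 1. Add chamber of origin to the VT characteristics collected.
2. Choose one of two routes:
   - Limit inclusion criterion 1 to patients in whom LV mapping is part of the planned clinical ablation.
   - Keep entry broad, and state that patients with no exit site in the 17 LV segments are left out of the exit-site test and of the LV-segment and innervation-map parts of Aims 3 and 4. Keep them for planar H/M and washout, HRV, and the patient and clinical VT predictors. Use the recorded chamber to separate an exit known to lie outside the LV from an LV exit that was not located.
3. Replace the pooled independent-sample t-test by a within-patient comparison of exit with other segments, for example a paired contrast of each patient's exit mean and other mean. A patient-level shift D then cancels, and a patient without an exit segment contributes no contrast.

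The cost is one data item, one eligibility line or analysis-set sentence, and a changed test. The first route may slow enrolment slightly. The second gives a smaller n for the LV-segment measures (for example 18 or 16 of 20), which should be reported as such. Under either route, the segmental results apply to LV VT only, which is all that those measurements cover.
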